#### STUDY TREATMENT

Study subjects will receive infusion at two study sites under the supervision of the site Principal Investigator or qualified co-investigator. Study product administration will be performed  $7 \pm 3$  days after randomization.

## Administration of Human Ischemia-Tolerant Allogeneic Mesenchymal Bone Marrow Cells (aMBMC)

The study will enroll a minimum of 20 subjects and will consist of 2 cohorts. Enrolled subjects will be randomized at 1:1 into an experimental group (n=10) or a placebo group (n=10). Subjects in the experimental group will receive 1.5 million cells per kg and subjects in the placebo group will receive 1 mL/kg LRS. At 90 days the placebo group will receive 1.5 million cells per kg and the initially treated group will receive 1 mL/kg LRS.

Once the subject is randomized into one of the two cohorts, the final formulation of aMBMC or placebo will be prepared. Within 8 hours of infusion, the appropriate number of cells will be thawed at the study site pharmacy and re-suspended in LRS at a concentration of  $1 \times 10^6$  cells/mL Subjects in placebo group will receive LRS at a volume of 1 mL/kg. The study solution (cells or placebo) will be labeled to indicate that it is an investigational agent and will contain subject's information, date, and time of formulation.

On the day of infusion, prior to study product administration, a skin test will be administered using 0.1 mL aliquot of the Final Formulation (Appendix C).

An intravenous line will be placed into an appropriate vein on the upper extremity and 0.9% sodium chloride solution will be run to keep the vein open. The study product will be drawn using an 18-gauge needle into a 60 mL syringe with an eccentric (offset) tip. The needle will be removed and infusion tubing will be attached to the syringe. The syringe with infusion tubing will be placed in a metered dose syringe pump positioned horizontally with the syringe rotated such that the syringe tip is at the lowest position. The product will be infused intravenously into the subject's arm at a constant rate of approximately 2 mL/min. The applicable volume for the target dose will be delivered within  $\pm$  2mL. Depending on subject's weight, up to three 60 ml syringes of product may be infused. After the entire product volume is delivered, 25mL of LRS (without cells) will be infused at 2ml/min to deliver cells from the infusion line for more accurate dosing. Subjects in the placebo group will receive intravenous LRS. Their syringes will be labeled as above to preserve blinding and followed by 25 ml of LRS infusion as above.

If the subject has an adverse reaction during the infusion, the infusion may be interrupted or slowed according to the severity of the reaction.

All appropriate treatment will be given to reduce any discomfort and ensure the subject's safety. The infusion may be restarted, if interrupted, if the subject is not considered to be at risk by the Investigator and the subject consents.

All subjects will receive the follow-up tests and evaluations as per Appendix A.

#### CONCOMITANT THERAPY AND CLINICAL PRACTICE

Subjects will continue all of their regular medications unless contraindicated. Subjects may be administered beta-blockers, ACE inhibitors or angiotensin receptors blockers, mineralocorticoid receptor antagonists, statin agents, or other medications, as tolerated.

## STATISTICAL METHODS

All randomized subjects who receive at least part of a dose of aMBMC or LRS will be included in the safety analysis. Subject safety data will be analyzed by actual dose level (i.e., number of cells/kg). Adverse events will be coded according to the MedDRA adverse event dictionary. The results will be tabulated to examine their frequency, affected organ systems, severity and relationship to study stem cell administration. The results of laboratory tests will be similarly evaluated. The efficacy analyses will include subjects that received the full dose of aMBMC or LRS and have the appropriate follow-up completed at the scheduled assessments (i.e., efficacy evaluable population). Safety measures include the composite of all-cause mortality, admission for worsening HF and all-cause admissions. Measurement of left ventricle end diastolic volume, left ventricle end systolic volume, left ventricular ejection fraction (LVEF), longitudinal strain and strain rate, global and segmental strain and strain rate, exercise capacity by 6 minute walk distance test, biomarkers, Kansas City Cardiomyopathy Questionnaire (KCCQ) and the New York Heart Association (NYHA) Classification will be completed in the entire efficacy evaluable population. A formal statistical analysis plan will be conducted in accordance with the guidelines of Good Clinical Practice (GCP), including the archiving of essential documents.

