## STUDY ENDPOINTS

#### **PRIMARY ENDPOINT**

#### Safety

Baseline and days 30, 60, and 90 post-initial infusion. After the crossover phase all patients will be evaluated at days 30, 60, and 90 days post the new infusion

- 1. Procedural complications
- 2. Vital signs
  - a. Temperature
  - b. Systolic blood pressure/diastolic blood pressure
  - c. Heart rate
  - d. Respiratory rate
  - e. Weight
- 3. Changes in heart failure medications
- 4. Clinical arrhythmias, defibrillator firing and anti-tachycardia pacing
- 5. Laboratory tests
  - a. CBC/PLT/differential
  - b. Chemistry-12, including liver function tests
  - c. Creatinine kinase
  - d. Troponin-I
- 6. Electrocardiogram
- 7. Composite of all-cause mortality all-cause admission and need for co-intervention. E.g. IV diuretics for worsening heart failure (RADIENCE trial criteria).

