# 4.2 Endpoints

## PRIMARY ENDPOINT

## Safety

Baseline and days 30, 60, and 90 post-initial infusion. After the crossover phase all patients will be evaluated at days 30, 60, and 90 days post the new infusion

- 8. Procedural complications
- 9. Vital signs
  - a. Temperature
  - b. Systolic blood pressure/diastolic blood pressure
  - c. Heart rate
  - d. Respiratory rate
  - e. Weight
- 10. Changes in heart failure medications
- 11. Clinical arrhythmias, defibrillator firing and anti-tachycardia pacing
- 12. Laboratory tests
  - a. CBC/PLT/differential
  - b. Chemistry-12, including liver function tests
  - c. Creatinine kinase
  - d. Troponin-I
- 13. Electrocardiogram
- 14. Composite of all-cause mortality all-cause admission and need for co-intervention. E.g. IV diuretics for worsening heart failure (RADIENCE trial criteria).

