#### 6.4 **Concomitant Medications and Rehabilitation**

Concomitant medications (any prescription and/or over-the-counter preparations) and therapies (nondrug or procedures) used by a subject while participating in this clinical trial will be optimized per AHA Guidelines and recorded at screening and until the end of the study or the end of a subject's participation in the study. Subjects may be administered beta-blockers, ACE inhibitors or angiotensin receptors blockers,

mineralocorticoid receptor antagonists, statin agents, or other medications, as tolerated. All other prescription and over-the-counter preparations approved by the patients' physician will be permitted.

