#### 7 STUDY ASSESSMENTS AND SCHEDULE

#### 7.1 **General Assessments**

## **Clinical Assessments**

- Complete medical history, including medication use and lifestyle history •
- Physical and cardiac examination, including vital signs (temperature, systolic blood pressure/diastolic • blood pressure, weight, heart rate, respiratory rate)
- Cardiac Examination •
- Composite of all-cause mortality, admission for worsening HF and all-cause admissions. •
- Exercise capacity: 6 minute walk distance •
- Kansas City Cardiomyopathy Questionnaire (KCCQ)(Appendix B)
- New York Heart Association (NYHA) Classification (Appendix B)

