## 7.3 Follow-up Assessments

## Day 30 (±7) days post-infusion

- Measure and record vital signs
- 12-lead ECG
- Pulse Oximetry
- 24 hour Holter ECG recording or ICD assessment
- Record the composite of all-cause mortality, admission for worsening HF and all-cause admissions, and concomitant medication use
- Physical and cardiac examination
- Clinical labs: serum chemistry including BUN & creatinine, CBC with diff, LFT's, total protein and albumin
- Cardiac biomarkers (CK and CK-MB fraction, troponin I)
- Serum/plasma stored for VEGF, FGF, NT-proBNP, troponin
- Kansas City Cardiomyopathy Questionnaire (KCCQ)
- New York Heart Association (NYHA) Classification
- 6 minute walk test

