#### 7.4 Early Termination Visit

- Measure and record weight and vital signs
- 12-lead ECG
- Pulse Oximetry
- 24 hour Holter ECG monitoring or ACD assessment
- Record the composite of all-cause mortality admission for worsening HF and all-cause admissions, and concomitant medication use
- Physical and cardiac examination
- Clinical labs: serum chemistry including BUN & creatinine, CBC with diff, LFT's, total protein and albumin
- Serum/plasma stored for VEGF, FGF, NT-proBNP, troponin
- Blood sample for IgA, IgE, IgG, IgM and for Lymphocyte Proliferation Panel
- 6 minute walk test
- Kansas City Cardiomyopathy Questionnaire (KCCQ)
- New York Heart Association (NYHA) Classification
- Cardiac MRI, with delayed contrast enhancement
- Full 2D and Doppler transthoracic echocardiography with speckle-tracking

The same follow-up visits will be performed after the crossover phase.

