#### APPENDIX A: SCHEDULE OF ASSESSMENTS

Visit	1	3	4	5	6	7	8	9	Early
Day	Days 1 to 2	Day 7±3	Day 30±7	Day 60±7	Day 90±7	Day 120±10	Day 150 ±7	Day 180±10	Termination
Informed Consent Form	Х								
IV Infusion		Х			X				
Final Formulation Skin Test *		Х			X				
Pregnancy Test ^	Х			~	Х			Х	Х
Troponin, HIV	Х								
Randomization into experimental or control group	Х								
Cardiac MRI	Х				X			Х	Х
Medical History	Х								
Spirometry/DLCO	Х				X			Х	
Full 2D Doppler transthoracic echocardiography with speckle-tracking †	Х				X			Х	Х
SF-36 Health Assessment, Canadian Cardiovascular Society (CCS) angina classification, KCCQ, NYHA	Х		X	X	X	Х	Х	Х	Х
Concomitant medications	Х		X	X	Х	Х	Х	Х	Х
12-lead ECG	Х	X	Х	Х	Х	Х	Х	Х	Х
24 hour Holter ECG recording*	Х		Х	Х	Х	Х	Х	Х	Х
Pulse Oximetry**	X	Х	Х	Х	Х	Х	Х	Х	Х
Vital Signs**	X	Х	Х	Х	Х	Х	Х	Х	Х
6 minute walk test	X		Х	Х	Х	Х	Х	Х	Х
Physical Examination	X	Х	Х	Х	Х	Х	Х	Х	Х
Cardiac Examination	Х	Х	Х	Х	Х	Х	Х	Х	Х
CBC with Diff	X		Х	Х	Х	Х	Х	Х	Х
Serum Chemistry with BUN/Creatinine, LFT	Х	Х	Х	Х	Х	Х	Х	Х	Х
VEGF, FGF, NT-proBNP	X	Х	Х	Х	Х	Х	Х	Х	Х
IgA, IgE, IgG, IgM and Lymphocyte Proliferation Panel		Х		Х	Х	Х	Х	Х	Х
Adverse Events		Х	Х	Х	Х	Х	Х	Х	Х
Cardiac Biomarkers (CK and CK-MB fraction, troponin I)	Х	Х	Х	Х	Х	Х	Х	Х	Х
Composite of all-cause mortality, myocardial infarction, coronary revascularization, and admission for worsening HF and all-cause admissions			X	Х	Х	Х	Х	Х	Х

† Ejection fraction must be ≤ 40%.
 ‡ A coronary angiogram performed during the index MI may be used to determine eligibility.

×Skin Test (Appendix C) to be performed prior to IV infusion

\*24 hour Holter ECG recording must be completed prior to IV infusion.

Collect 5mL of blood into tube for lymphocyte proliferation panel prior to IV infusion. Provide 2mL of serum in another tube of IgA, IgE, IgG and IgM test. Serum is taken from blood in 5mL tube, which is centrifuged for 15 minutes at 3500 RPM.

\*Vital signs taken every 2 hours after infusion and pulse oximetry taken continuously for 2 hours after IV infusion. Vital signs include temperature, blood pressure, heart rate respiratory rate and weight †† A test will be taken prior to IV infusion to establish baseline. Another test will be taken 6 hours ± 30 minutes after infusion. If levels are significantly elevated, two more tests will be taken every 6 hours for the next 12 hours.

Need continuous ECG monitoring during infusion

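### The primary safety composite includes need for co-intervention where it is defined, but not where it is recorded or described for analysis, so subjects treated for worsening heart failure without admission can go uncounted

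*Combined protocol and SAP*

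**What the plan says.** The composite appears in three forms.

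- **Endpoint definition.** The Synopsis primary endpoint list (item 7) has "Composite of all-cause mortality all-cause admission and need for co-intervention. E.g. IV diuretics for worsening heart failure (RADIENCE trial criteria". Section 4.2 (item 14) repeats it, including "need for co-intervention. E.g. IV diuretics for worsening heart failure (RADIENCE trial criteria".
- **Short form.** The Synopsis Statistical Methods give "Safety measures include the composite of all-cause mortality, admission for worsening HF and all-cause admissions", and Section 7.1 lists "Composite of all-cause mortality, admission for worsening HF and all-cause admissions". The Day 30 visit in Section 7.3 says "Record the composite of all-cause mortality, admission for worsening HF and all-cause admissions, and concomitant medication use". Day 60 and Day 90 carry the same line, and Section 7.4 has it for early termination: "Record the composite of all-cause mortality admission for worsening HF and all-cause admissions, and concomitant medication use". Section 7.4 also says that the same visits follow the crossover infusion.
- **Schedule form.** The row in Appendix A reads "Composite of all-cause mortality, myocardial infarction, coronary revascularization, and admission for worsening HF and all-cause admissions".

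Section 9 says that tables will cover every safety and efficacy outcome measure, and Section 9.2 says that all safety outcomes will be summarized. Neither restates the composite. Section 9 also says that a detailed SAP will be written before the data are analysed.

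**The concern.** Safety is the primary objective, and this composite is one of the listed primary safety items. The component that drops out is the only one that picks up a decompensation managed without a hospital stay. Inclusion is limited to NYHA class II-III, where such management is plausible. A site that works from the visit lists has no prompt to record the event as part of the composite. An analyst who works from the Statistical Methods has no instruction to count it. If the cells caused this kind of worsening, the composite would understate it. With 10 subjects per group, one or two subjects change the descriptive picture.

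**Working it through.** The plan states no event rate for the composite, and Section 9.4 says that the sample size does not rest on power. There is no figure to reproduce, so the check is a comparison of definitions followed by an illustration of scale.

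**Step 1: which subjects differ.** Let D be death, A any admission, H admission for worsening heart failure, and C co-intervention.

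- Endpoint definition: D or A or C.
- Short form: D or H or A. Every H is also an A, so this reduces to D or A.
- Difference: subjects with C who have neither D nor A.

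Every subject counted by the short form is counted by the definition, but not the reverse. The plan does not use the word outpatient. It follows from the structure: treatment given during an admission already counts as an admission, so C adds only events without one.

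**Step 2: Appendix A.** Myocardial infarction and revascularization would nearly always involve admission and so add few subjects, if any. C is still absent.

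**Step 3: other records.**

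- Section 8.1.1 and the paragraph on pre-existing conditions in Section 8.2.3 make worsening heart failure an adverse event. Section 8.2.2 has such events sought by questioning at each contact and recorded with dates, severity and action taken.
- Section 6.4 says that drugs and therapies "will be optimized per AHA Guidelines and recorded at screening and until the end of the study". Because therapy is also being optimized, a recorded drug change does not by itself show worsening.
- Neither section says which records become composite events.

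**Step 4: scale, on assumed rates.** Suppose a share p of the 20 subjects has C without D or A during the study, independently of one another. The expected number uncounted is 20p, and the chance of at least one is 1 - (1 - p)^20.

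| p (assumed) | Expected uncounted | Chance of at least one |
|---|---|---|
| 2% | 0.4 | 33% |
| 5% | 1.0 | 64% |
| 10% | 2.0 | 88% |
| 20% | 4.0 | 99% |

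**Step 5: effect on the difference between products, first period, 10 against 10.** Assume other death or admission in 5% of each group, worsening that needs treatment at rates w1 (cells) and w0 (placebo), a share f of it treated without admission, and independence. The full difference is 0.95(w1 - w0), and the short-form difference is that times (1 - f).

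| w1 vs w0 (assumed) | Full | f = 20% | f = 50% | f = 80% |
|---|---|---|---|---|
| 30% vs 10% | 19.0 points | 15.2 | 9.5 | 3.8 |
| 10% vs 5% | 4.75 points | 3.8 | 2.4 | 0.95 |

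The opposite case also exists. If admissions are 25% against 10% and a share o of each group is treated without admission, the short form shows 15 points and the full form 15(1 - o), which is 13.5 points at o = 10%. Leaving C out does not always shrink the difference.

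**The case against.** The other side has four good arguments.

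1. The Statistical Methods list is introduced as inclusive, and Sections 9 and 9.2 promise a summary of all safety outcomes. The full composite is therefore nominally covered. This stands: a reader might infer that co-intervention has been removed from the analysis, and the documents do not say that. They give conflicting component lists and do not say which governs.
2. IV diuretics for worsening heart failure should leave a dated adverse event and a matching therapy record. This largely stands, and a SAP could write the linking rule. It would still depend on adverse event entries that were not made with the composite in mind.
3. The case report forms are not in the documents, so a visit list without a reason for drug changes does not show that the form lacks one. This stands.
4. A reader might infer that the DSMB would not see such events, because Section 8.6 commits the sponsor to sending it serious adverse events. The documents do not support that. The same section gives the board ongoing review of safety data, and Section 8.1.2 lets an event without hospitalization be judged serious.

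It is also fair that the repeated visit line is one piece of wording used several times, and that Appendix A seems to carry text from another protocol. A count of places is therefore weak evidence of intent. The conflict itself remains.

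**Conclusion.** The concern holds as a conflict between stated rules for one primary safety item. Under the visit lists and the Statistical Methods, the composite equals or undercounts the defined endpoint. The subjects at issue are those treated for worsening heart failure who neither died nor were admitted.

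The size is unknown. Every figure in Steps 4 and 5 rests on assumed rates and shows only what the gap could amount to. A reader might infer that a particular share of events would be lost, or that the safety assessment fails. Neither follows. The analysis is mainly descriptive and no decision rule uses this composite. Other safety records cover much of the same ground. This is a point to consider: low in severity, and cheap to put right before data collection.

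**What to change.** 1. Use the endpoint definition in the Synopsis Statistical Methods, Section 7.1, the visit lists in Sections 7.3 and 7.4, and Appendix A. Write out the co-intervention criteria instead of citing a trial by name, with IV diuretics as an example and not as the only qualifying therapy. In Appendix A, list myocardial infarction and coronary revascularization as separate rows.
2. Add one item at each post-infusion visit: co-intervention for worsening heart failure without admission since the last visit, yes or no, with treatment and date.
3. In Section 9.2, tabulate the composite, each component, and a death-or-admission row, by product and by 90-day period counted from the infusion that opens it.

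A reason for every heart failure drug change would help interpretation but is optional.

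The cost is aligned wording and one form item per visit, with no added visit or test. Co-intervention is a softer clinician judgement than admission, in a single-blind trial. It can also slightly dilute a difference if it is equal between products. The separate component and death-or-admission rows deal with both.

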## ABBREVIATIONS

Abbreviation	Definition
AE	Adverse event
AHA	American Heart Association
ALT	Alanine amino transferase
AST	Aspartate amino transferase
BMMNC	Bone marrow mononuclear cells
BUN	Blood urea nitrogen
CBC	Complete blood count
СК	Creatine kinase
CRF	Case report form
CRP	C-reactive protein
CVD	Cardiovascular disease
ECG	Electrocardiogram
FDA	Food and Drug Administration
FGF	Fibroblast growth factor
GCP	Good Clinical Practice
HF	Heart failure
ICF	Informed consent form
ICH	International Conference on Harmonization
IgA	Immunoglobulin A
lgE	Immunoglobulin E
lgG	Immunoglobulin G
IgM	Immunoglobulin M
IND	Investigational New Drug
IRB	Institutional Review Board
KCCQ	Kansas City Cardiomyopathy Questionnaire
LFT	Liver function test
LVEF	Left ventricular ejection fraction
MACE	Major adverse cardiac events
aMBMC	Allogeneic mesenchymal bone marrow cells
MedDRA	Medical Directory for Regulatory Activities
N-IHF	Non-ischemic heart failure
NT-proBNP	N-Terminal Prohormone of Brain Natriutic Peptide
NYHA	New York Heart Association Classification
SAE	Serious adverse event
SDF-1	Stromal derived factor 1
STEMI	ST segment elevation myocardial infarction
VEGF	Vascular Endothelial Growth Factor

## BACKGROUND

## 1.1 Non-Ischemic Heart Failure

Heart failure (HF) is a major cause of morbidity and mortality worldwide, affecting in the United States more than 5.1 million people. Projections show that by 2030, the prevalence of HF will increase 25% from 2013 estimates. The lifetime risk of developing HF is 20% for Americans ≥40 years of age. In the United States, HF incidence has largely remained stable over the past several decades, with >650,000 new HF cases diagnosed annually. HF incidence increases with age, rising from approximately 20 per 1,000 individuals 65 to 69 years of age to >80 per 1,000 individuals among those >85 years of age. In 2009, HF as an underline cause of mortality was 56,410.

Non-ischemic cardiomyopathy is defined as disease of the myocardium associated with mechanical or electrical dysfunction exhibiting inappropriate ventricular hypertrophy or dilatation. There are numerous causes leading to non-ischemic cardiomyopathy. Non-ischemic cardiomyopathy may be either primary or secondary to systemic diseases. In this study we will evaluate patients with dilated cardiomyopathy, which is a primary mixed disease, who have heart failure symptoms. Prevalence of non-ischemic HF (N-IHF), in large-scale therapeutic trials the proportion of patients with N-IHF ranged from 18% to 53%. There is a relation between sex, age and etiology of HF; non-ischemic cardiomyopathy is more frequent in women and in younger individuals. The prognosis for HF is poor, with an overall mortality of 50% within 4 years, and a 1-year mortality of 50% in patients with severe HF. Although the prognosis of N-IHF was shown to be better than that in IHF, mortality is high in N-IHF reported from 23% in 1 year, 48% in 2 years and 60% in 5 years. Although there has been some progress in the past decades in the treatment of HF by using pharmacological therapy, surgery and device-based therapy, current interventional and pharmacological therapies for HF have limits and the need for a more efficient regenerative therapeutic strategy is urgent. This treatment could delay disease progression and reduce mortality and morbidity by helping injured myocardium recovery and/or facilitating cardiac repairing and regeneration.

